Study Intervention Description	
The following will be offered to all female youth (N=1200):
 
 (1) HIV Testing Services (HTS) via home-based or community based recruitment strategies (2) HIV testing approaches that females can choose from include: (a) oral fluid HIV self-testing (OraQuick ADVANCE® Rapid HIV-1/2 Antibody Test, OraSure Technologies) at their convenience; (b) staff-aided testing at home/mobile site; and (c) a referral to a health care facility where HIV testing will be done by a health care provider (standard facility-based HTS) (3) Behavioral survey at baseline visit (4) SMS HIV test experience satisfaction survey (5) Staff-administered questionnaire about self-testing for females who choose self-testing option. 
For all HIV positive females:
 
All HIV positive females will receive the following;
 
 (1) Point of care (POC) CD4 cell count at baseline (2) Viral load testing using dried blood spot (DBS) at 0 and 12 months (3) Referral for care and treatment; Adaptive linkage to care intervention. All HIV positive participants (N≈108) will be randomized to receive standard referral (N≈54) or standard referral plus SMS message (N≈54) to link to HIV care and treatment services; those who do not link to care within 2 weeks will be re-randomized in a ratio of 1:1 to a second SMS message or a one-time economic incentive to link to care.

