Primary Objectives	
(1) To determine the preferred recruitment venue and testing modality that targets and finds the highest number of HIV infected and at risk female youth aged 15-24 years in Homa Bay County, Nyanza region, western Kenya (Aim 1).
 
 • This will be determined by examining the uptake and yield of previously undiagnosed HIV infection of the two (2) 'seek' strategies (community or home-based) and the three (3) 'test' strategies (self-testing, HTS in a home/mobile setting, or facility-based HTS) among female youth; 
(2) To conduct an economic evaluation, using cost effectiveness analyses to determine the relative utility of each seek, test, link, and prevention intervention (Aim 3).

Secondary Objective	
(1) To pilot and evaluate an adaptive intervention to link newly diagnosed HIV-positive female youth to treatment and care services (Aim 2a);
 
(2) To identify barriers and facilitators to seeking HIV care services after receiving a positive diagnosis (Aim 2b);
 
(3) To identify barriers and facilitators to seeking HIV prevention services for high risk female youth after receiving a negative HIV test result (Aim 2c);

	(4) To provide an HIV prevention intervention to a randomly selected subset of high risk negatives (N≈185) (motivational text message, with referral for combination prevention interventions), and to re-test them at 12 months (Aim 2d).

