There are numerous examples of individual HIV prevention interventions aimed at addressing the drivers of the HIV epidemic among youth. In the MP3 Youth study (data not yet published), we successfully reached 1740, recruited 1093 youth between the ages of 15-24 years old, carried out HIV testing for 1074, linked 69.7% of newly diagnosed HIV positives to care, and enrolled 284 for follow-up (HIV positive cohort: 106; PrEP cohort: 28; CCT cohort: 50, and HIV negatives: 100). From MP3 Youth, we learnt that we can reach and recruit youth in a mobile health care setting. In the GIRLS study, we will learn whether we can reach and recruit female youth in a home-based setting as well. In MP3 Youth we demonstrated that we were able to successfully test youth in a mobile health event setting, but unlike in the GIRLS study, MP3 Youth did not offer alternative options to staff provided rapid HIV testing, such as self-testing or referral to a health facility. In addition, although we successfully linked HIV infected participants in the MP3 Youth study to care and treatment using a one-time economic incentive (i.e., bus fare), the MP3 Youth study did not have SMS reminders as a linkage strategy. We were able to successfully verify school enrollment for the CCT cohort and will use similar procedures in the GIRLS study for linkage verification.

The Government of Kenya recently approved pre-exposure prophylaxis (PrEP) use as a national strategy for HIV prevention among key populations including high-risk females (Mukoma, 2016, NASCOP, 2015). PrEP is an HIV prevention method by which an uninfected individual takes antiretroviral drugs prior to HIV exposure to reduce the risk of infection (Plosker, 2013). Homa Bay is one of the selected counties that will offer PrEP, therefore, referrals will be made to government, private and NGO facilities offering the approved HIV prevention services, which includes PrEP.

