Offering linkage to care after a positive HIV test is critical – for risk reduction and lifesaving ART initiation. Data show that sexual risk behaviors decrease after a positive test and ART initiation, but over time these risky behaviors may begin all over again (Allen et al., 2003; Bunnell et al., 2006; Colfax et al., 2002). Of Kenyans 15-64 years old self-reported as positive, 79.4% enrolled in care services within 90 days of diagnosis (NASCOP, 2014a). Previous studies in Uganda and South Africa showed 90% uptake of HTS and linkage among adults, but adolescents were not included; effective strategies need to be identified for them as barriers likely differ. Two strategies that were key to linkage were found to be POC CD4 and follow-up with participants (Barnabas et al., 2014). Evidence of SMS effectiveness for supporting linkage to and retention in HIV care exists (Finocchiaro-Kessler et al., 2014; Lester et al., 2010) for adults and we incorporate SMS elements in our study to assess impact for female youth.

Kenya is developing a new electronic tracking system using SMS messaging to facilitate linkage and retention in care and adherence to ARVs for people living with HIV, and messages for high-risk HIV-negatives. This national platform envisions use of mobile phones via the SMS platform for communication among facilities, health care workers, and patients to track and support linkage, treatment adherence, adherence to prevention interventions, and retention for improved outcomes. Data generated by this research in the use of SMS to engage participants (while maintaining their privacy and confidentiality) will inform this planned national platform and guide improvements of the system.

Rationale for unconditional cash transfer

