These findings demonstrate that UCT can improve important outcomes such as delayed marriage and childbearing, but there may be a trade-off, between these desired behaviors and improved educational outcomes. In our study, we offer a one-time unconditional cash transfer for a subset of participants (i.e., those who do not link to care after the first randomization in the adaptive linkage to care pilot) because adolescents who test positive may experience structural barriers (i.e. transportation costs) in linking to care in a timely manner. Linkage is a one-time event and we assume that newly diagnosed HIV positive female youth will link to care within two weeks after the first randomization (standard referral vs. standard referral and SMS). The two-week timeframe for linkage to care is defined by the national government; those identified as HIV infected should be started on treatment during this period. In the study we will track if the participants have linked during this two-week time frame and will analyze time to linkage to HIV care and treatment services. We will also explore the use of the economic incentive for linkage during the face-to-face (or telephone) exit interview which will be conducted at 12 months. If a phone interview is conducted, participant's identity will be confirmed by asking the participant to provide three names used at enrollment as well as their current age, so that her identity may be ascertained correctly.

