11.6.1 Linkage to Care Intervention

We will use an adaptive intervention/SMART trial design methodology to compare the success of a) short message service (SMS) text messaging and b) economic incentive (transport reimbursement worth KSh 400) systems in linking to HIV care and treatment services participants who test positive for HIV (expected N≈108) and require augmented linkage support. The initial intervention (first randomization) is that participants who test positive for

HIV gets a standard referral or standard referral plus an SMS message with instructions on where to seek care. Some participants may engage in HIV care after receiving either the referral or referral plus SMS. Subsequently, the intervention will be tailored so those participants who are not linked to care within 2 weeks after the initial intervention, who will be randomized again to receive either follow-up SMS with linkage encouragement, or a one-time economic incentive to seek care (shown to be effective in previous studies (Handa et al., 2014)). All HIV positive participants enrolled for follow up will receive a motivational SMS with adherence to medication and care messages and an SMS survey at intervals of 3 months for 12 months.

At 12 months, we will follow-up with those participants that tested positive and enrolled in care to measure their viral load to determine whether they have been linked, retained in care and are adhering to treatment. We will also conduct an interview at 12 months to determine barriers and facilitators for linkage to care and treatment.

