The field study coordinator will provide a list of study ID numbers of participants needing allocation. The study statistician or data manager will record the unique study identification number and the date of the assignment on the allocation list, and relay the assignment to the field study coordinator. Alternatively, if we find that this is not efficient during implementation of our study, we will pursue other methods, such as using sequentially numbered, sealed envelopes containing participant allocation that may be prepared beforehand (Doig & Simpson, 2005).

We anticipate a total of 108 HIV positive participants to be randomly assigned to either standard referral or standard referral plus SMS at the first randomization. Participants not linked to care after the first randomization will be re-randomized in a 1:1 ratio to receive either another SMS text or an economic incentive.

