With this estimate of the expected percentage of girls with newly diagnosed HIV infection, we asked how small of an increase in the odds of newly diagnosed HIV infection could be detected with 80% power when community-based recruitment is compared to home-based recruitment. With 600 youth recruited by each strategy, power is 80% to detect an odds ratio of 1.67, in other words, a modest increase from 9% to 14% newly diagnosed with HIV infection. When comparing testing approaches, and assuming an equal proportion of girls prefers each approach and testing approach does not interact with recruitment strategy, power is 80% to detect an odds ratio of 1.85. If there is an interaction between recruitment strategy and testing approach, when comparing

testing approaches within a recruitment strategy (i.e., estimating simple main effects), power is 80% to detect an odds ratio of 2.32.

These calculations show the proposed sample size (N=1200) is capable of detecting modest differences in the yield of newly diagnosed HIV infection across both recruitment strategies and testing approaches.

Among the approximately 108 female youth we expect to be newly diagnosed with HIV infection, about 20% are expected to successfully initiate HIV care at a health facility after a single SMS message. The remaining 80% (N=86) who are not linked to care after the initial SMS message will be randomly assigned to either continued SMS messages or to economic incentives. Assuming at least 60% are linked to care at some point during follow-up, survival analysis employing Cox regression will be able to detect a hazard ratio of 2.2 describing the impact of treatment condition (continued SMS vs. economic incentives) on the occurrence and timing of successful linkage to care at a health facility, with 80% power.

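### The linkage power text leaves out the first randomisation, referral versus referral plus SMS has no clearly specified analysis, and the 60% linkage has no stated cut-off

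*Combined protocol and SAP*

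**What the plan says.** The design sections describe two randomisations. Section 6 states: "All HIV positive participants (N≈108) will be randomized to receive standard referral (N≈54) or standard referral plus SMS message (N≈54"), with 1:1 re-randomisation of those not linked within two weeks. Sections 11.6.1 and 15.12 and Appendix A agree; 11.6.1 says: "We anticipate a total of 108 HIV positive participants to be randomly assigned to either standard referral or standard referral plus SMS". It also expects some linkage in both arms: "Some participants may engage in HIV care after receiving either the referral or referral plus SMS".

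The power text in section 15.11 describes something else. It expects about 20% of all 108 to link after one SMS, and continues: "The remaining 80% (N=86) who are not linked to care after the initial SMS message will be randomly assigned to either continued SMS messages"; the other arm receives incentives. It then assumes that at least 60% link at some unspecified time in follow-up, and states 80% power for a hazard ratio of 2.2 between continued SMS and incentives.

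The analysis text in section 13.2 (Adaptive Intervention Pilot) describes linkage among responders to the initial SMS and among girls in each augmented arm. It directs the survival comparison at continued SMS versus incentives. Table 1 lists a Cox comparison of two conditions with N≈108 but does not name them. Its linkage timeline runs two weeks, one week to re-randomise, and two more weeks, five in total. Section 15.10 refers to Table 1 for analysis timing, while section 6 gives 12 months of follow-up.

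The aim is secondary: "To pilot and evaluate an adaptive intervention to link newly diagnosed HIV-positive female youth to treatment and care services (Aim 2a").

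**The concern.** Three things do not fit together.

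- **Power text and design.** Section 15.11 treats every girl as having had an initial SMS, although about half are randomised to referral alone. For their non-linkers, a second-stage SMS is a first message, not a continued one. No referral-only linkage rate is given, and no stratification of the second stage by first assignment is planned.
- **The first-stage contrast.** In section 7.4 the protocol says "we incorporate SMS elements in our study to assess impact for female youth". The three-monthly motivational messages go to everyone followed in the HIV-positive cohort. The first randomisation is therefore the only randomised SMS versus no-SMS comparison of linkage, and no section clearly says how it will be analysed.
- **The cut-off.** The 60% supplies the events behind the power claim, but it is tied neither to Table 1's five weeks nor to 12 months.

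At stake is how the pilot can be read. Without a named contrast, time origin and cut-off, these could be chosen after the data are seen. The primary objectives are not affected.

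**Working it through.** **1. The plan's own figure.** Inputs: 1,200 × 9% = 108 (section 10.2); 108 × 0.80 = 86.4, 60% linked and HR 2.2 (section 15.11); 1:1 allocation (section 15.12). Alpha is not stated for this calculation; two-sided 0.05 is assumed.

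- Events needed (Schoenfeld): 4(1.960 + 0.842)² / (ln 2.2)² = 50.5.
- Events available: 0.60 × 86 = 51.6.
- Power: Φ(√51.6/2 × ln 2.2 − 1.960) = Φ(0.87) = 0.808.

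The figure reproduces, with the 60% applied to the 86.

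**2. The pool under the two-stage design.** With 20% linkage on referral plus SMS and r on referral alone, N = 54(1 − r) + 54 × 0.80. Values of r are assumed, and 60% of N is taken as linked.

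| r | N re-randomised | Events | Power at HR 2.2 |
|---|---|---|---|
| 0% | 97.2 | 58.3 | 85% |
| 10% | 91.8 | 55.1 | 83% |
| 20% | 86.4 | 51.8 | 81% |
| 30% | 81.0 | 48.6 | 78% |

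N=86 corresponds to r = 20%, that is, no first-stage SMS effect. The stated power is not sensitive to this.

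**3. Mix within the second-stage SMS arm.** If both first-stage arms link 20%, referral-only non-linkers number 54 × 0.80 = 43.2. Half of them, 21.6, go to SMS. About 22 of the 43 girls in that arm then receive a first message and the rest a second one.

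**4. What the first-stage contrast can show.** With 54 per arm, two-sided 0.05 and a pooled-variance test of two proportions, 20% versus 10% gives Φ[(0.10√54 − 1.960√(2 × 0.15 × 0.85)) / √(0.09 + 0.16)] = 0.305, or about 31%. The corresponding hazard ratio is ln 0.8 / ln 0.9 = 2.12. Events are 54 × 0.30 = 16.2 and the 95% factor is exp(1.96 × 2/√16.2) = 2.65, so the interval is about 0.8 to 5.6. The 10% is an assumption.

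**5. The cut-off behind the 60%.** Under proportional hazards with HR 2.2, if the SMS arm has linked a proportion s by the cut-off, the incentive arm has linked 1 − (1 − s)^2.2. Setting the average of the two to 0.60 gives s = 0.459 and 0.741. If analysis stopped two weeks after re-randomisation, the 60% would need about 46% on SMS and 74% on incentive within those two weeks, among girls who had not linked before. Over a longer window the same proportions are easier to reach.

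**The case against.** Much of the case on the other side stands. HR 2.2 reproduces and survives a wide range of referral-arm rates, so section 15.11 reads as stale wording more than a faulty calculation. Section 11.6.1 states the aim as SMS versus incentive in girls needing augmented support, and that comparison is specified and powered. Table 1's N≈108 matches the first-stage population, so its unnamed conditions could be read as covering the first-stage arms. The aim is a pilot and need not carry a powered first-stage test. The sentence quoted from section 7.4 sits under a heading on engagement and retention, although it follows on from evidence about linkage as well.

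Three stronger readings are tempting and not supported.

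- **That the second stage is underpowered.** Suppose the SMS arm links 20% per two weeks at a constant hazard. Two weeks after re-randomisation, linkage is 20% and 1 − 0.8^2.2 = 38.8%, giving 43 × 0.588 = 25.3 events and 51% power. That needs both a two-week cut and a rate that appears nowhere in the documents. At 12 weeks the same hazard gives 73.8% and 94.7%, 43 × 1.685 = 72.5 events and 92% power. Linkage can be ascertained late, through clinic record review, SMS surveys and the exit interview. Table 1's five weeks is a data-collection timeline and is not stated as a censoring rule.
- **That first-stage linkage will far exceed 20%.** The previous study "linked 69.7% of newly diagnosed HIV positives to care", but with a bus-fare incentive, no SMS and no stated window, so this is not a rate for referral or a single SMS. Section 7.4's "we assume that newly diagnosed HIV positive female youth will link to care within two weeks after the first randomization" explains the national timeframe and gives no rate; taken literally, it would leave nobody to re-randomise.
- **That no first-stage comparison exists at all.** The linkage endpoint and Table 1's Cox row could be read to include one. The defect is that neither says so.

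**Conclusion.** The concern holds as a specification problem that should be fixed; it is not an arithmetic error. Section 15.11 does not describe the two-stage design, and N=86 agrees with that design only if referral alone also links about 20%. The stated power is right on its inputs (80.8%) and moves only between 85% and 78% for referral-arm linkage of 0% to 30%. Referral versus referral plus SMS has no clearly specified analysis and would be imprecise if analysed (about 31% power for 20% versus 10%). The second-stage SMS arm could be roughly half first messages and half second, with no stratification planned. The 60% is plausible under longer follow-up and demanding at two weeks, and the documents do not say which cut-off applies. These results assume two-sided 0.05, proportional hazards and the illustrative linkage rates shown. The consequence is confined to a secondary pilot aim.

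**What to change.** 1. Add a Cox or log-rank comparison of referral versus referral plus SMS in all of the roughly 108 girls as randomised. Time it from the first randomisation and censor at a fixed cut-off that precedes re-randomisation and applies equally to girls who are never re-randomised. Report the estimate with its confidence interval and label it low-powered.
2. Time the second-stage Cox comparison from re-randomisation, and stratify by or adjust for first-stage arm.
3. Rewrite section 15.11 for the two-stage design, with a linkage assumption for each first-stage arm. Reconcile the 60% with Table 1 by stating one analysis cut-off. Restate the detectable hazard ratio only if the cut-off is two weeks after re-randomisation.
4. Name the two conditions in Table 1's linkage row.

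The cost is protocol and SAP wording plus one extra analysis of assignments and linkage dates already being collected, with no new participants or data. The downside is that the first-stage estimate will be imprecise and must be presented so, and the stated second-stage power could become less favourable once a cut-off is fixed.

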15.12 Randomization

Our study is observational in nature, but the Aim 2a adaptive linkage to care intervention does contain a randomization component. Newly diagnosed HIV-positive females identified in our study will be randomized to receive standard referral to link to care or standard referral plus SMS message to link to care. Those that do not successfully link to care will then be re-randomized to receive either an SMS message or an economic incentive. We will utilize an approach called permuted blocks randomization for participant assignment to the intervention. Permuted block randomization has several advantages, one of which is promoting equal distribution of participants in each group. A list of random allocations will be generated by the study statistician in randomly ordered permuted blocks of either 2, 4, 6, 8 or 12 allocations. The allocation list will be stored in a password protected file which will only be accessible to the study statistician, data manager or project manager.

The field study coordinator will provide a list of study ID numbers of participants needing allocation. The study statistician or data manager will record the unique study identification number and the date of the assignment on the allocation list, and relay the assignment to the field study coordinator. Alternatively, if we find that this is not efficient during implementation of our study, we will pursue other methods, such as using sequentially numbered, sealed envelopes containing participant allocation that may be prepared beforehand (Doig & Simpson, 2005).

We anticipate a total of 108 HIV positive participants to be randomly assigned to either standard referral or standard referral plus SMS at the first randomization. Participants not linked to care after the first randomization will be re-randomized in a 1:1 ratio to receive either another SMS text or an economic incentive.

See Section13: Statistical Considerations and Section 18: Data Handling and Record Keeping.

16. QUALITY CONTROL AND QUALITY ASSURANCE

A co-principal investigator who is a Kenyan physician with clinical research experience, the project manager, and IRDO internal research auditor who is a clinician (Clinical Officer) with extensive experience overseeing quality assurance in numerous clinical trials have been identified as the monitors to conduct Quality assurance/Quality control for the study. Following written standard operating procedures as they appear in the study specific operating procedures (SSP) and this protocol, the monitor will verify the study is conducted and data are generated, documented (recorded) and reported in compliance with the protocol, IRB, government of Kenya regulations, DAIDS and any other regulatory requirements. Details about data specific QA/QC are provided in the data management SOP. Also the study specific protocols contain built-in QA/QC procedures per intervention.

